#### **8.1.1.1 Initial tumor scans**

Initial tumor scans at screening must be performed within 28 days prior to day 1 of cycle 1. The site study team must review screening scans to confirm the patient has measurable disease per RECIST 1.1.

Tumor scans performed as part of routine clinical management are acceptable for screening if they are of acceptable diagnostic quality and performed within 28 days of day 1 of cycle 1.

If brain scans are performed to document the stability of existing metastases, the brain MRI should be acquired during screening. If MRI is medically contraindicated, CT with contrast is an acceptable alternative.

#### **8.1.1.2 Tumor scans during the study**

The first on-study scan assessment should be performed at 6 weeks ( $\pm 2$  weeks; starting from cycle 1 day 1). Subsequent tumor scans should be performed every 6 weeks ( $\pm 2$  weeks) or more frequently if clinically indicated. Scan timing should follow calendar days and should not be adjusted for delays in cycle starts.

All supplemental imaging must be collected.

Objective response should be confirmed by repeat scan performed at least 4 weeks after the first indication of a response is observed. Patients will then return to the regular scan scheduled, starting with the next scheduled time point. Patients who receive additional scans for confirmation do not need to undergo the next scheduled scan if it is fewer than 4 weeks later; scans may resume at the subsequent scheduled time point.

When radiological disease progression is identified by the investigator in clinically stable patients, disease progression is to be confirmed by another set of scans performed 4 to 8 weeks later, per iRECIST guidelines in section [8.1.1.5](#).

If disease progression is not confirmed, clinically stable patients are to continue study interventions until progression is confirmed. Patients are to return to their regular scan schedule. If the next scheduled scan will occur in less than 4 weeks, this scheduled scan may be skipped.

If disease progression is confirmed, study interventions will be discontinued. Exceptions are detailed in section [8.1.1.5](#).

#### **8.1.1.3 End of treatment and follow-up tumor imaging**

If patients discontinue study interventions, tumor scans should be performed at the time of discontinuation ( $\pm 4$ -week window) unless previous scans were obtained within 4 weeks of discontinuation. If patients discontinue study interventions due to documented disease progression, this is the final required tumor scan if the investigator elects not to implement iRECIST.

---

If patients discontinue study interventions without documented disease progression, every effort should be made to monitor disease status by acquiring tumor scans using the same schedule used while on treatment (every 6 weeks [ $\pm$ 2 weeks]).

Scans are to be continued until one of the following conditions are met:

- Disease progression identified by the investigator (radiological progression per [i]RECIST [1.1] or mCRPC-specific progression)
- Start of a new anti-cancer treatment
- Pregnancy of the patient
- Withdrawal of consent by the patient
- End of the study

For clinically unstable patients, a scan obtained within 2 weeks after clinical progression is recommended. Scans are to be continued as per regular schedule (section [1.3](#)).

#### **8.1.1.4 RECIST 1.1 assessment of disease**

RECIST 1.1 will be used as the primary measure for assessment of tumor response, date of disease progression, and as a basis for all Protocol guidelines related to disease status (e.g., discontinuation of study interventions).

#### **8.1.1.5 iRECIST assessment of disease**

iRECIST is based on RECIST 1.1 but adapted to account for the unique tumor response seen with immunotherapeutic drugs. iRECIST will be used by the investigator to assess tumor response and progression and make treatment decisions. When clinically stable, patients may continue study interventions beyond RECIST 1.1 progression with continued assessment of response according to the rules outlined in section [10.2](#). iRECIST reflects that some patients can have a transient tumor flare after the start of immunotherapy, then experience subsequent disease response. This data will be captured in the clinical database.

- If the patient is clinically stable, continue study interventions per Protocol
  - Continue scans per Protocol schedule (the next scheduled scan should be  $\geq$ 4 weeks from most recent scan acquired)
  - Continue investigator assessment per iRECIST
  - Collect scans

• If the patient is not clinically stable, best medical practice is to be applied

For the purpose of this decision process, lack of clinical stability is defined as:

- Unacceptable toxicity
- Clinical signs or symptoms indicating clinically significant disease progression
- Decline in performance status
- Rapid disease progression or threat to vital organs or critical anatomical sites (e.g., central nervous system metastasis, respiratory failure due to tumor compression, spinal cord compression) requiring urgent alternative medical intervention

### **8.1.1.6 PD-1 treatment progression**

PD-1 treatment progression is defined by meeting all of the following criteria:

1. Has received at least 2 doses of an approved anti-PD-1/L1 mAb
2. Has demonstrated disease progression after PD-1/L1
3. Progressive disease has been documented within 12 weeks from the last dose of anti-PD-1/L1 mAb
  - 3.1. Progressive disease is determined according to iRECIST
  - 3.2. This determination is made by the investigator. Once progressive disease is confirmed, the initial date of disease progression documentation will be considered the date of disease progression.

## **8.2 Safety assessments**

If patients feel unwell at any point in time during the study after being discharged from the hospital, they should contact their study investigator as indicated in the ICF.

### **8.2.1 Physical examinations, ECOG performance status, body height, and body weight**

General physical examination with organ/system-specific physical examination will be carried out by a licensed physician (or the physician's assistant or a nurse practitioner).

For screening, a complete physical examination will be performed including head (eyes, ear, nose, and throat), neck, cardiovascular, chest/lungs, abdomen (including liver and spleen size), extremities, neurological, skin, and lymph nodes. For subsequent visits, a physical examination is to be done with the focus on abdomen (including liver and spleen size), lymph nodes, and any other system that may contribute to clinical disease assessments.

An ECOG performance status will be assigned as indicated in the [Schedule of activities](#).

Body height and body weight will be measured. Body height will be measured only at screening. Body weight will be measured before the start of each treatment cycle and as indicated in the [Schedule of activities](#).

### **8.2.2 Vital signs**

Vital signs will include blood pressure (systolic and diastolic, after  $\geq 5$  minutes of rest), body temperature, heart rate, and respiratory rate.

### **8.2.3 Special assessments on treatment days**

#### **8.2.3.1 Cycle 1 day 1**

Patients will be observed in the hospital up to 12 hours following nanrilkefusp alfa administration. Vital signs (systolic and diastolic blood pressure after  $\geq 5$  minutes of rest, body temperature, heart rate, and respiratory rate) will be documented at the following frequency at minimum unless clinically required otherwise:

- Before nanrilkefusp alfa administration
- 15 minutes ( $\pm 5$  minutes) after nanrilkefusp alfa administration

---

- 30 minutes ( $\pm 5$  minutes) after nanrilkefusp alfa administration
- 2 hours ( $\pm 15$  minutes) after nanrilkefusp alfa administration
- 4 hours ( $\pm 30$  minutes) after nanrilkefusp alfa administration
- 12 hours ( $\pm 2$  hours) after nanrilkefusp alfa administration

#### **8.2.3.2 Cycle 1 day 2, day 8, and day 9; and treatment days of cycle 2**

Patients will be observed in the hospital up to 4 hours following nanrilkefusp alfa administration. Vital signs (systolic and diastolic blood pressure after  $\geq 5$  minutes of rest, body temperature, heart rate, and respiratory rate) will be documented at the following frequency until discharge:

- Before nanrilkefusp alfa administration
- 15 minutes ( $\pm 5$  minutes) after nanrilkefusp alfa administration
- 30 minutes ( $\pm 5$  minutes) after nanrilkefusp alfa administration
- 2 hours ( $\pm 15$  minutes) after nanrilkefusp alfa administration
- 4 hours ( $\pm 30$  minutes) after nanrilkefusp alfa administration

#### **8.2.3.3 Treatment days of cycle 3 and onwards**

Patients will be observed in the hospital up to 2 hours following nanrilkefusp alfa administration. Vital signs (systolic and diastolic blood pressure after  $\geq 5$  minutes of rest, body temperature, heart rate, and respiratory rate) will be documented at the following frequency until discharge:

- Before nanrilkefusp alfa administration
- 15 minutes ( $\pm 5$  minutes) after nanrilkefusp alfa administration
- 30 minutes ( $\pm 5$  minutes) after nanrilkefusp alfa administration
- 2 hours ( $\pm 15$  minutes) after nanrilkefusp alfa administration

#### **8.2.4      Electrocardiography and left ventricular ejection fraction**

During the study, patients with signs or symptoms of chest pain, murmurs, gallops, irregular rhythm, or palpitations must be further assessed if clinically indicated, including the need for hospitalization. Standard 12-lead ECG will be done locally at the site for assessment of any change in QTcF interval and other parameters.

Left ventricular ejection fraction will be assessed using either echocardiography or multigated acquisition scanning (MUGA). However, the method chosen needs to stay the same throughout the trial.

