## 1.2 Schema

## 1.3 Schedule of activities

### 1.3.1 Schedule of activities, nanrilkefusp alfa combined with pembrolizumab

Cycle	Visit	Cycle 1 and cycle 2						From cycle 3 onwards				End of treatment  Within 7 (+7) days after the last dose of nanrilkefusp alfa and/or pembrolizumab (whichever occurs later)	Follow-up	
		Screening Up to 28 days before day 1 of cycle 1	Day 1	Day 2	Day 6	Day 8	Day 9	Day 13	Day 1	Day 2	Day 8	Day 9		
Informed consent 		X												
Demography 		X												
Cancer  and medical history		X												
Height		X												
Pregnancy test		X (blood)	X (urine or blood) 						X (urine or blood) 				X (urine or blood) 	
Physical examination		X	X 	X 	X	X 	X 	X	X 	X 	X 	X 	X	X 
Body weight		X	X 						X 				X	
Vital signs		X	X 	X 	X	X 	X 	X	X 	X 	X 	X 	X	X 
Urinalysis 		X	X 			X 			X 		X 		X	
Electrocardiography		X	X 						X 				X	
Left ventricular ejection fraction 		X	End of each second cycle (i.e., cycle 2, 4, 6...; allowed interval from day 9 of the current cycle to day 2 of the next cycle)									X		
Eastern Cooperative Oncology Group performance score		X	X 						X 				X	X 
Tumor assessment (CT/MRI/bone scan)		X 	Every 6 weeks ( $\pm$ 2 weeks) starting from day 1 of cycle 1 until disease progression identified by the investigator, start of a new anti-cancer treatment, pregnancy of the patient, withdrawal of consent by the patient, or end of the study											
Nanrilkefusp alfa administration 			X	X	X	X			X	X	X	X		
Pembrolizumab administration 			Every 3 weeks (day 1) according to the prescribing information											
Tumor biopsy 		X	X											
Adverse events		X	X											X 
Concomitant medication/ non-drug therapies		X	X											X 
Survival information														X 

---

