1. Criteria for discontinuation of study interventions are listed in section 7.1. In case nanrilkefusp alfa needs to be discontinued for reasons other than disease progression, pembrolizumab treatment can continue for up to a total of 35 administrations (approximately 2 years) in patients without disease progression or unacceptable toxicity. A schedule of activities for patients who continue pembrolizumab after discontinuation of nanrilkefusp alfa is shown in section 1.3.2. In case pembrolizumab needs to be discontinued, nanrilkefusp alfa treatment can continue until disease progression or unacceptable toxicity and the schedule of activities for patients receiving nanrilkefusp alfa combined with pembrolizumab will apply (not applicable in the Czech Republic). In the Czech Republic: In case pembrolizumab needs to be discontinued, nanrilkefusp alfa treatment will be discontinued as well.
2. No study-specific procedures are to be performed before ICF signature.
3. Age at screening and gender
4. Primary tumor location, histology/cytology, initial diagnosis date, lines of previous treatment, start and stop dates of the treatments before this study, any prior mutations/genetic analysis (e.g., EGFR, ALK mutations), and the date of the latest disease progression if not coinciding with the stop date
5. Before nanrilkefusp alfa administration
6. Every 30 ( $\pm 2$ ) days until 120 ( $\pm 2$ ) days after the last dose of pembrolizumab or 30 ( $\pm 2$ ) days after the last dose of nanrilkefusp alfa, whichever is later
7. Before nanrilkefusp alfa administration and afterwards as clinically required
8. Follow-up visits 30 ( $\pm 2$ ) days and 90 ( $\pm 2$ ) days after the last dose of nanrilkefusp alfa and/or pembrolizumab (whichever occurs later)
9. Before and after nanrilkefusp alfa administration as described in section 8.2.3
10. In case of proteinuria  $\geq 100$  mg/dL at screening, a 24-hour urine analysis will have to be performed (before the start of nanrilkefusp alfa treatment) to document 24-hour proteinuria levels and a urine test will continue during the treatment period. In case of increase of proteinuria with  $\geq 300$  mg/dL (at any time), a 24-hour urine analysis will be performed.
11. Using either echocardiography or MUGA; the method chosen needs to stay the same throughout the trial

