### 4.3 Justification for dose

#### 4.3.1 Nanrilkefusp alfa

The planned dose of nanrilkefusp alfa for this study is 12 µg/kg body weight on days 1, 2, 8, and 9 every 3 weeks, which is the recommended phase 2 dose defined based on the totality of data generated in study SC103 (AURELIO-03) entitled “A multicenter open-label phase 1/1b study to evaluate the safety and preliminary efficacy of SO-C101 as monotherapy and in combination with pembrolizumab in patients with selected advanced/metastatic solid tumors”.

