### **6.5 Dose modification and toxicity management**

#### **6.5.1 Dose modification and toxicity management for nanrilkefusp alfa**

Dose modification and toxicity management for nanrilkefusp alfa for safety reasons will be discussed on a case-by-case basis between the site and the sponsor's medical monitor.

Transient pyrexia is a frequent AE after nanrilkefusp alfa injection. The use of, e.g., ibuprofen, and other non-steroid premedication can be considered according to local standard practice for prevention and treatment of fever.

Recommendations for clinical management of cytokine release syndrome are provided in section [6.5.3](#).

To minimize the risk for injection site reaction, subcutaneous injection sites should be rotated to different areas of the body (upper and lower extremities, each of the 4 quadrants of the abdomen).

To minimize the risks associated with shortening of the QT interval, vital signs and ECG must be closely monitored as per Protocol and institutional guidelines.

Liver function tests for nanrilkefusp alfa toxicity evaluation in this study will include AST, ALT, total bilirubin, and alkaline phosphatase.

Nanrilkefusp alfa-related hepatic toxicities should be managed as shown in [Table 6.2](#).

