10.0 Conventions and Derivations

10.1 Study Treatment

The study treatment defined is the combination of SOT101 12 µg/kg subcutaneously and 200 mg pembrolizumab IV infusion.

Patients will be treated with SOT101 12 µg/kg subcutaneously on day 1 (± 1 day for the cycle start), day 2, day 8, and day 9 in combination with pembrolizumab 200 mg IV on day 1 in 3-week cycles.

Pembrolizumab will be administered as an IV infusion via peripheral or central venous line starting within 30 minutes after the first dose (day 1) of SOT101 in each 3-week cycle.

Start of study treatment is defined as the date and time of first dose of either SOT101 or pembrolizumab, whichever occurs earliest. Per protocol this should be SOT101.

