12.8.5.2 Electrocardiogram

Summaries will be generated for patients based on International Council for Harmonization (ICH) E14 category, with QTcF in categories <450msec, 450-480msec, or increased to value >480 and ≤500 msec, and value >500 msec, and patients with CFB in QTcF increased by ≤30 msec, >30 to ≤60 msec, and by >60 msec.

The actual values and CFB for each scheduled study visit for selected ECG parameters will be plotted at each time point up to and including cycle 10 using a box-whisker plot including an overlaid mean profile line.

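### Every scheduled on-treatment ECG is taken before the day 1 injection, about 13 days after the last one from cycle 2 on, so the ECG data cannot detect an acute QTcF effect in either direction

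*Protocol*

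**What the plan says.** ECG findings are part of the secondary safety endpoint (Protocol section 3). Section 8.2.4 gives their purpose: "Standard 12-lead ECG will be done locally at the site for assessment of any change in QTcF interval and other parameters". It names no time point and leaves timing to the schedule of activities.

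The ECG row in Protocol 1.3.1 has entries at screening, on day 1 of cycles 1 and 2, on day 1 from cycle 3 onwards, and at End of treatment. Each day 1 entry carries footnote 5, which reads "Before nanrilkefusp alfa administration". There is no ECG entry on days 2, 6, 8, 9 or 13.

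Nanrilkefusp alfa is given "on days 1, 2, 8, and 9 every 3 weeks" (Protocol 4.3.1).

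On QT risk, Protocol 6.5.1 states: "To minimize the risks associated with shortening of the QT interval, vital signs and ECG must be closely monitored as per Protocol". The sentence goes on to name institutional guidelines as well.

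SAP 12.8.5.2 tabulates QTcF by category and adds: "The actual values and CFB for each scheduled study visit for selected ECG parameters will be plotted at each time point", up to cycle 10.

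**The concern.** The protocol names QT shortening as a risk to be followed closely by ECG, and says the ECG is there to pick up any QTcF change. Its own schedule never times an ECG to an injection. Other measurements are timed to dosing: vital signs are taken at 15 and 30 minutes and 2 hours in every cycle, at 4 hours in cycles 1 and 2, and at 12 hours on cycle 1 day 1. PK sampling starts 30 minutes after the first dose.

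At stake is how the safety tables will be read. The SAP does not say that its on-treatment ECG summaries are trough values. A flat plot of change from baseline could be taken as showing no QT effect, when it shows only that nothing persisted to the end of the dosing interval.

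**Working it through.** No sample size, power or error rate is involved. The check is calendar arithmetic on the schedule, then a sensitivity calculation on an assumption.

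**1. Which scheduled ECGs are on treatment.** SAP 10.6 ends the on-treatment period on the day before the End of treatment visit. That leaves only the day 1 ECGs, all pre-dose. SAP 10.2 takes baseline as the last value before first dosing, so the cycle 1 day 1 ECG is itself a baseline reading. On-treatment change from baseline therefore comes from cycle 2 onward. In plots to cycle 10 that is at most 10 − 1 = 9 ECGs per patient, every one pre-dose.

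**2. Gap between the last injection and the next day 1 ECG.** The next day 1 is day 22 of the current cycle, so gap = 22 − day of last injection. The window is plus or minus "1 day for the cycle start" (SAP 10.1).

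| Last injection given | Gap (days) | With window |
|---|---|---|
| Day 9 | 22 − 9 = 13 | 12–14 |
| Day 8 | 22 − 8 = 14 | 13–15 |
| Day 2 | 22 − 2 = 20 | 19–21 |

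Held doses and delayed cycles lengthen the gap further.

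**3. End of treatment ECG.** Its timing is "Within 7 (+7) days after the last dose of nanrilkefusp alfa and/or pembrolizumab (whichever occurs later"), so 0 to 14 days after the last dose of either drug. It occurs once and is not tied to an injection. For a patient who continued pembrolizumab alone, it may fall long after the last injection.

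**4. Drug remaining at the pre-dose ECG.** The documents give no half-life for nanrilkefusp alfa, so this is an assumption shown over a range. Fraction remaining = 0.5^(hours ÷ half-life); 13 days = 312 hours and 7 days = 168 hours.

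| Assumed half-life | Left at 13 days | Left at 7 days |
|---|---|---|
| 12 h | 0.0000015% | 0.006% |
| 24 h | 0.012% | 0.8% |
| 48 h | 1.1% | 8.8% |
| 72 h | 5.0% | 19.8% |
| 120 h | 16.5% | 37.9% |

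Up to a half-life of about two days, little drug remains at the day 1 ECG. Beyond that the statement weakens. Residual drug is also not the same as residual effect.

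**5. QTcF categories.** SAP 12.8.5.2 groups absolute QTcF below 450 msec, at 450–480, above 480 to 500, and above 500. It groups change as increases of up to 30, above 30 to 60, and above 60 msec. Neither set separates out a short QTcF or a decrease. Only the plots of actual values and change could display one. This holds whenever the ECG is taken.

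**The case against.** A reader might infer that the ECG endpoint cannot show any effect of nanrilkefusp alfa. The documents do not support that. A pre-dose ECG can show a persistent or cumulative change, the End of treatment ECG may fall within days of an injection, and absence of drug at 13 days rests on a half-life that is not given.

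The other points on that side are these:

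- Section 6.5.1 does not rest on the scheduled ECG alone. It also cites vital signs, which are taken post-dose, and institutional guidelines. Section 8.2.4 calls for further assessment of patients with cardiac signs or symptoms. This is fair, but symptom-driven assessment would miss a silent QTcF change, and neither source yields scheduled visits for the SAP plots.
- The sparse schedule was a reasoned choice. The amendment summary says ECGs were reduced because no significant cardiac toxicity had been seen in a 13-week monkey study or in clinical studies. The reduction is not an error. The current text of 6.5.1 and 8.2.4 still asks more of the ECG than the current schedule delivers.
- Analyses are descriptive, and neither document says that the tables will support a claim of no QT effect. This is correct; the risk is one of misreading.
- No time of peak concentration is given, so 2 or 4 hours is not shown to be the peak. On day 1 pembrolizumab also follows within 30 minutes, so a post-dose ECG there reflects both drugs.
- SAP 6.1 records that recruitment stopped after the August 2023 futility analysis. This limits what re-timing can achieve, but not the SAP changes.

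**Conclusion.** The concern holds for acute effects. All scheduled on-treatment ECGs are pre-dose on day 1, and from cycle 2 on they come about 13 days after the last injection (12 to 14 with the window, more if doses are missed or held). They cannot detect an acute or peak-exposure QTcF effect in either direction, although they can show a persistent one. Protocol 1.3.1 therefore conflicts with what 6.5.1 and 8.2.4 expect of the ECG.

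The timing result rests only on the schedule. How little drug remains at those ECGs depends on the assumed half-life and is secure only up to about two days. The missing categories for QTcF decreases are an additional gap, independent of timing.

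**What to change.** **Protocol.** Reconcile the ECG row and footnote in 1.3.1 with 6.5.1 and 8.2.4. Move at least one already scheduled later day 1 ECG, for example cycle 2, from pre-dose to the post-dose observation point already used for vital signs and PK (4 hours on cycle 2 day 1). Keep screening and cycle 1 day 1 as baseline.

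**SAP 12.8.5.2.**
- Summarise pre-dose and post-dose ECGs separately, including any unscheduled post-dose ECGs.
- Show the actual time since the last injection. A fixed label of 12 to 14 days would be wrong for cycle 1 day 1, for missed or held doses, and for patients on pembrolizumab alone.
- State that pre-dose values do not assess acute QTcF effects.
- Add categories for decreases to the QTcF change table.

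**Cost.** A footnote change, one SAP sentence, a split table and extra categories, with no added ECG or visit. The pre-dose ECG is lost at the moved visit; no dosing rule in the protocol was found that depends on it. Cycle 1, the first exposure, still has no post-dose ECG. With recruitment stopped, re-timing reaches only patients still on treatment, whereas the SAP changes apply to all data.
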